#### 5.2.2 Secondary Endpoints

- Population mean estimates of drug clearance (CL), volume of distribution of the central compartment ( $V_c$ ), absorption rate constant ( $K_a$ ), volume of distribution of the peripheral compartment ( $V_p$ ), intercompartmental clearance (Q), the maximum plasma concentration ( $C_{max}$ ), the area under the plasma concentration-time curve over a dosing interval ( $AUC_{0-tau}$ ), the average concentration during a dosing interval at steady-state ( $C_{av,ss}$ ), and the plasma concentration immediately prior to dosing ( $C_{trough}$ ) for TAK-935.
- Percentage of subjects with at least 1 markedly abnormal value for clinical laboratory evaluations, vital signs, and electrocardiogram (ECG) parameters after TAK-935 treatment.

CONFIDENTIAL

### 5.2.3 Exploratory Endpoints

CCI

## 6.0 STUDY DESIGN AND DESCRIPTION

### 6.1 Study Design

This phase 1b/2a, multicenter, randomized, double-blind, placebo-controlled, parallel-group, dose-escalation study with an open-label part is designed to examine the safety, tolerability, PK, and PD of TAK-935 as adjunctive therapy in adult subjects with a diagnosis of developmental and/or epileptic encephalopathies. This study will be conducted at approximately 11 sites in North America with experience in conducting clinical studies in patients with rare epilepsies.

Adult subjects (aged  $\geq 18$  and  $\leq 65$  years) with a diagnosis of developmental and/or epileptic encephalopathies demonstrating bilateral motor seizures (ie, drop seizures, tonic-clonic, tonic, bilateral clonic, atonic, myoclonic-atonic, myoclonic-tonic-clonic, focal seizures with bilateral hyperkinetic motor features) (average of  $\geq 2$  per month during the past 3 months) based on the investigator's assessment will be enrolled. The study will screen a sufficient number of subjects to ensure approximately 20 randomized subjects.

At the Screening Visit (Visit 1), informed consent and/or assent (if applicable) is obtained from the subjects and/or subjects' legally acceptable representative. Subjects will then undergo screening procedures to assess study eligibility in accordance with the study entry criteria (see [Appendix A](#) and Sections 7.1 and 7.2). CCI

The 4-week Baseline Period CCI can begin as soon as informed consent has been signed. At the end of the 4-week Baseline Period and after confirmation of eligibility, subjects will return to the clinic on Day 1 in Part 1 (Visit 2) for randomization. If a subject does not meet the eligibility criteria during the Screening/Baseline Period, the subject will be discontinued from the study (screen failure).

The study will consist of 2 parts:

- Part 1 is a randomized double-blind part consisting of 3 periods: a screening/baseline period (4-6 weeks), titration period (20 days), and maintenance period (10 days). The target final dose of 300 mg BID will be reached after a 20-day titration period.
- Part 2 is an open-label continuation part consisting of 4 periods: a titration period (10 days), maintenance period (44 days), de-escalation period (3-6 days) and follow-up period (30 days).

Part 1 of the study is designed to investigate the safety, tolerability, PK, and PD in adult subjects with developmental and/or epileptic encephalopathies in a double-blind manner. Efficacy CCI

CCI during the 4-week Baseline Period will be randomly assigned on

Day 1 (Visit 2) to receive TAK-935 (n=16) or matching placebo (n=4) twice daily (BID) orally or via stable gastrostomy tube (G-tube)/ percutaneous endoscopic gastrostomy (PEG) tube for 30 days during the Double-Blind Treatment Period. Subjects will initiate IP (investigational product; TAK-935 or placebo) at 100 mg BID from Days 1 through 10. Subjects who cannot tolerate the 100 mg BID dosing will be withdrawn from the study. On Day 11 (Visit 3), subjects will return to the clinic and the IP dose will be increased to 200 mg BID; this dose level will be maintained from Days 11 through 20 but may be reduced to 100 mg BID in subjects who cannot tolerate the 200 mg BID dose or demonstrate safety concerns, based on the investigator's judgment and in consultation with the subject's caregiver, when applicable. On Day 21 (Visit 4), subjects will return to the clinic; at this visit, the investigator will review the subject's safety data and will discuss the benefit-risk with the subject or subject's legally acceptable representative before proceeding to increase the dose from 200 mg BID to 300 mg BID, and this dose level will be maintained from Days 21 through 30. The dose may be reduced to 200 mg BID in subjects who cannot tolerate the 300 mg BID dose or demonstrate safety concerns, as described above. Subjects for whom the dose was reduced to a lower dose level will stay on that dose level until the end of the Double-Blind Treatment Period. Three days after each dose up-titration or de-escalation, subjects will be contacted by phone to monitor study drug compliance, concomitant medication use, and AEs. Any change in dose will be documented in the subject's clinic chart and the subject's caregiver will be advised to note the same in the dosing card.

On Day 1 (Visit 2), PK, PD, AED, and optional PGx blood samples will be collected before the morning dose of study drug. PK and PD blood samples also will be collected at 1, 3, and 5 hours after the morning dose on Day 1. On Day 11 (Visit 3) and Day 21 (Visit 4), PK and PD blood samples (before and approximately 1 hour after morning dose), an AED blood sample (before morning dose), and seizure diary data will be collected.

Subjects who are unwilling to continue into Part 2 of the study will proceed directly to the Final Visit (at Day 31), including dose de-escalation, as appropriate, followed by the 30-day Follow-up Period.

Part 2 of the study is designed to investigate the safety, tolerability, PK, and PD of TAK-935 in adult subjects with developmental and/or epileptic encephalopathies in an open-label manner. All subjects who complete the Double-Blind Treatment Period in Part 1 will have the option to continue directly into the Open-Label Treatment Period in Part 2. Because some subjects may enter Part 2 after receiving placebo and others TAK-935 up to 300 mg BID and to maintain the study blind, all subjects will start on TAK-935 200 mg BID at the start of Part 2. On Day 31 (Visit 5), subjects will return to the clinic and receive TAK-935 200 mg BID from Days 31 to 40 but may be reduced to 100 mg BID in subjects who cannot tolerate the 200 mg BID dose or demonstrate safety concerns, based on the investigator's judgment and in consultation with the subject's caregiver, when applicable. Subjects who cannot tolerate the 100 mg BID dose or demonstrate safety concerns, based on the investigator's judgment and in consultation with the subject's caregiver, will be discontinued from the study. On Day 41 (Visit 6), subjects will return to the clinic; at this visit, the investigator will review the subject's safety data and will discuss the benefit-risk with the subject or subject's legally acceptable representative before proceeding to

increase the dose from 200 mg BID to 300 mg BID, and this dose level will be maintained until the Final Visit (Visit 7) for the dose de-escalation phase. Subjects' dose may be increased or decreased before Day 41 (Visit 6) based on clinical condition (ie, increasing seizures) and investigator judgment. This dose may be reduced to 200 mg BID in subjects who cannot tolerate the 300 mg BID dose or demonstrate safety concerns, as described above. Subjects for whom the dose was reduced to a lower dose level will stay on that dose level until the Final Visit (Visit 7) for the dose de-escalation phase. Three days after each dose up-titration or de-escalation, subjects will be contacted by phone to monitor study drug compliance, concomitant medication use, and AEs. Any change in dose will be documented in the subject's clinic chart and the subject's caregiver will be advised to note the same in the dosing card.

On Day 31 (Visit 5), PK, PD, AED, and PGx (if collected on Day 1) blood samples will be collected before the morning dose of study drug and seizure data will also be collected. On Day 41 (Visit 6), PK, PD, and AED blood samples will be collected before the morning dose of study drug and seizure data will also be collected.

On Day 85 (Visit 7), subjects will return to the clinic for the Final Visit and enter the 3- or 6-day de-escalation phase. At this visit, PK, PD, and AED blood samples will be collected before the morning dose of study drug and seizure data will also be collected. Subjects will then enter the dose de-escalation phase and will be instructed to follow the applicable de-escalation dosing schedule outlined below:

- For subjects on 300 mg BID during the maintenance phase, the dose will be de-escalated to 200 mg BID for 3 days (Days 85-87) and subsequently to 100 mg BID for 3 days (Days 88-90).
- For subjects on 200 mg BID during the maintenance phase, the dose will be de-escalated to 100 mg BID for 3 days (Days 85-87).
- For subjects on 100 mg BID during the maintenance phase, there is no de-escalation and the dose is discontinued on Day 85.

Immediately after the last dose is the 30-day Follow-up Period comprised of a Follow-up Phone Call (Visit 8) on Day 91 and a Follow-up Visit (Visit 9) on Day 121. At the Follow-up Visit, subjects will return to the clinic for study procedures including PD and AED blood sample collection.

In Parts 1 and 2, subjects will be instructed to not take their morning dose of study drug or concomitant AEDs on the days of scheduled study visits to facilitate collection of the predose PK, PD, AED, and optional PGx blood samples. The morning dose of study drug and concomitant AEDs will be administered in the clinic on these study days after laboratory samples are collected. For subjects who are not able to come for the visit during the morning hours, they should be instructed to take their morning dose, as usual, and come to the study site during the afternoon hours, as feasible for the subject. While in the clinic, the site should attempt to obtain 2 PK samples, separated by 1-2 hours, if possible. Hours since the last dose of the study medication must be recorded in the eCRF upon collection of the PK sample(s).

[figure not shown]
Seizure data will be recorded daily in the seizure diary by each subject and/or subjects' caregiver throughout the Screening/Baseline Period up until the Follow-up Visit (Visit 9) on Day 121 and will be collected from the diary at each visit.

The investigator, in consultation with the sponsor, may decide to reduce the TAK-935 dose at any time during the study in the event of any safety or tolerability concerns.

Any subject who prematurely withdraws from the study should proceed directly to the Final Visit (at time of withdrawal), including dose de-escalation, as appropriate, followed by the 30-day Follow-up Period.

A schematic of the study design is shown in [Figure 6.a](#). A schedule of study procedures is listed in [Appendix A](#).

Figure 6.a Schematic of Study Design

Note 1: Circled numbers denote study visits.

Note 2: Subjects will remain on stable background AED therapy throughout the study.

Note 3: Starting doses for Parts 1 and 2 are shown; individual subject doses may be reduced to the previous dose level if there are safety and tolerability concerns at new dose level.

Note 4: Maintenance dose levels (ie, 100, 200, or 300 mg BID) will be de-escalated at the end of the maintenance phase of Part 2, depending on the dose subjects are taking at that time (ie, if at TAK-935 300 mg BID level, reduce to 200 mg BID for 3 days followed by 100 mg BID for 3 days; if at the 200 mg BID level, reduce to 100 mg BID for 3 days; if at the 100 mg BID level, there is no de-escalation).

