### 9.1.11 Procedures for Clinical Laboratory Samples

Blood and urine samples are to be collected at the time points stipulated in the Schedule of Study Procedures (Appendix A). Blood samples for hematology and serum chemistry tests are to be collected after an overnight fast of  $\geq 8$  hours, if possible. Samples will be collected in accordance with acceptable laboratory procedures. Details of these procedures and required safety monitoring will be given in the laboratory manual.

For an individual subject, the maximum volume of blood collected at any single visit will be approximately 71 mL, and the approximate total volume of blood collected over the course of the study will be 230 mL (Table 9.a).

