**Table 9.a Approximate Blood Volume**

Sample Type	Sample Volume (mL)	Number of Samples (a)			Total Volume (mL)
		Screening Visit	Part 1	Part 2	
HIV, HBsAg, HCV (b)	6	1	---	---	6
HCV RNA detection by qPCR (c)	6	1	---	---	6
FSH (d)	(d)	1		1	(d)
Estradiol (e)	2	1		1	4
Serum chemistry (f)	6	1	1	2	24
Hematology	2	1	1	2	8
Plasma sample for TAK-935 PK analysis	4	---	8	3	44
Plasma sample for AED analysis	4	---	3	3	28
Plasma sample for PD analysis (g)	4	2	16	6	104
Blood sample for DNA PGx	6	---	1	---	6
Blood sample for RNA PGx (g)	2.5	---	2	2	10
Total Blood Volume (mL)					240

--- =not applicable.

(a) Does not include blood draws at any unscheduled visits.

(b) One 2-mL blood sample for each test.

(c) Subjects who are positive for hepatitis C Ab should return to the clinic for an unscheduled visit to provide a blood sample for HCV qPCR.

(d) For diagnostic purposes in female subjects only; sample will be run from serum chemistry volume (no extra volume required).

(e) In female subjects only.

(f) Includes serum pregnancy test for female subjects of childbearing potential.

(g) Two blood samples per scheduled time.

The clinical laboratory tests to be performed are listed in [Table 9.b](#).

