**Table 9.c**      **Collection of Plasma Samples for Measurement of TAK-935 and M-I in Plasma**

Study Part	Study Day/Visit	Scheduled Time
Part 1	Day 1	Before and 1, 3, 5 hours after morning dose
	Days 11 and 21	Before and ~1 hour after morning dose
Part 2	Day 31, 41, and 85	Before morning dose

Subjects and/or subjects' caregivers will be instructed to not administer the morning dose of study drug on Days 11, 21, 31, 41, and 85. On these days, the predose (ie, within 30 minutes prior to dosing) blood sample will be collected at the same time point as the blood samples for clinical laboratory tests. The morning dose of study drug will be administered immediately after the predose PK blood samples have been collected. The exact date and time of last morning and evening study drug doses before each scheduled visit, the exact time of study drug dose taken in the clinic, the exact time of the last meal relative to dosing, and exact time of the PK blood draws will be recorded on the source document and eCRF.

For subjects who are not able to come for the visit during the morning hours, they should be instructed to take their morning dose, as usual, and come to the study site during the afternoon hours, as feasible for the subject. While in the clinic, the site should attempt to obtain 2 PK samples, separated by 1-2 hours, if possible. Hours since the last dose of the study medication and the exact time of the last meal relative to dosing must be recorded in the eCRF upon collection of the PK sample(s).

Instructions for the collection, handling, and shipping of plasma PK samples are provided in the Laboratory Manual.

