**CONFIDENTIAL**

**Appendix A Schedule of Study Procedures (continued)**

Study Day	Screening/ Baseline Period (a)	Part 1: Double-Blind Treatment Period (b)			Part 2: Open-Label Treatment Period (b)			Follow-up Period (c)	
	Days -41 to 0	Day 1	Day 11	Day 21	Day 31	Day 41	Day 85 (c,d)	Day 91	Day 121
Visit Window (days)			±2	±2	±2	±2	±2	±2	±2
Visit Number	1 Screening Visit	2	3	4	5	6	7 Final Visit	8 Follow-up Phone Call	9 Follow-up Visit
Neurological exam, including funduscopy and visual acuity (if possible) (k)	X			X			X		
12-lead ECG	X	X			X		X		
Clinical laboratory tests (l)	X	X			X		X		
CCI									
CCI									
Plasma sample for TAK-935 PK (m,n)		X	X	X	X	X	X		
Plasma sample for AED analysis (n,o)		X	X	X	X	X	X		X
Plasma sample for PD (n,p)	X	X	X	X	X	X	X		X
Blood sample for DNA PGx (q)		X							
Blood sample for RNA PGx (n,r)		X			X				
Access IVRS/IWRS for subject ID/medication ID/subject status (s)	X	X	X	X	X	X	X		
Assess benefit-risk analysis with subject and caregiver before increasing dose to 300 mg BID				X					
Dispense study drug with dosing card (t)		X	X	X	X	X	X		
In-clinic administration of morning dose of study drug (u)		X	X	X	X	X	X		

(Footnotes follow table.)

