(k) Any clinically significant abnormalities noted prior to administration of study drug should be described and recorded on the Medical History form. Any clinically significant changes in the neurological examination noted after administration of study drug should be captured on the AE page of the eCRF.

(l) Hematology, serum chemistry, and urinalysis tests. If urine cannot be collected due to the subject's cooperation or because the subject is wearing a diaper, it is acceptable for the subject to continue in the study and the reason should be documented in the source document.

(m) PK plasma samples for measurement of TAK-935 and M-I concentrations will be collected before and 1, 3, and 5 hours after the morning dose on Day 1; before and approximately 1 hour after the morning dose on Days 11 and 21; and before the morning dose on Days 31, 41, and 85.

(n) On Days 11, 21, 31, 41, and 85, subjects should visit the clinic in the morning prior to taking their morning dose. For subjects who are not able to come for the visit during the

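### Chemistry and hematology on Days 11, 21 and 41 would cut the wait for the first scheduled on-drug test from 30 (TAK-935) or 54 (former placebo) dosing days to 10, at blood draws already planned

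*Protocol*

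**What the plan says.** **Dosing.** Protocol 6.1 gives 100 mg BID on Days 1-10, 200 mg BID on Days 11-20 and 300 mg BID on Days 21-30. Everyone entering Part 2 takes TAK-935 200 mg BID from Day 31 and 300 mg BID from Day 41. At Day 21 the investigator reviews the subject's "safety data and will discuss the benefit-risk with the subject" or representative before the increase, and the same review is required at Day 41. Visit-day samples precede the morning dose.

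**Laboratory schedule.** Section 9.1.11 states: "Blood and urine samples are to be collected at the time points stipulated in the Schedule of Study Procedures". That schedule (Appendix A) marks clinical laboratory tests at Screening and on Days 1, 31 and 85. Footnote (l) defines them as "Hematology, serum chemistry, and urinalysis tests". Table 9.a agrees, with one chemistry and one hematology sample at Screening, one of each in Part 1 and two of each in Part 2.

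**Text that does not match.** Section 9.1.18.1 lists Days 11, 21, 31, 41 and 85 and says that on these days the predose "blood sample will be collected at the same time point as the blood samples for clinical laboratory tests". Section 9.1.11 adds that details of the procedures and "required safety monitoring will be given in the laboratory manual".

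**Where the results are used.** Section 7.5 stops study drug at numeric ALT/AST limits at any time during treatment. The percentage of subjects with a markedly abnormal laboratory value is part of a secondary endpoint (5.2.2).

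**The concern.** This is a dose-escalation study whose primary objective is safety and tolerability. Its liver stopping limits need a laboratory value before they can act. One of them (above 5 x ULN for more than 2 weeks) also needs repeat values, and the 9.1.11 retest starts only after a first abnormal result. If no test is scheduled during escalation, a symptom-free change goes unseen unless someone orders an unscheduled test, and the Day 21 review has no scheduled on-drug chemistry or hematology to draw on. Former placebo subjects are in the same position at Day 41, because their Day 31 sample is taken before their first TAK-935 dose.

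A site reading 9.1.18.1 could expect laboratory draws on Days 11, 21 and 41. A site reading Appendix A would make none.

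**Working it through.** No power or sample-size formula applies; the check is a day count and a blood-volume count. Counts assume the planned course without dose reduction.

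**1. Dosing days before the first scheduled on-drug test** (predose draws, so test day minus first dosing day)
- TAK-935: 31 - 1 = 30 days, matching the plan's 30-day double-blind period: 10 each at 100, 200 and 300 mg BID. With the ±2-day window, 28 to 32.
- Former placebo: 85 - 31 = 54 days, matching the plan's 10 + 44 days in Part 2: 10 at 200 and 44 at 300 mg BID. With both visit windows, 50 to 58.

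**2. Cross-check with Table 9.a.** Chemistry 4 x 6 = 24 mL and hematology 4 x 2 = 8 mL, as printed. This fits four laboratory visits, not the seven that draws on Days 11, 21 and 41 would give.

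**3. Effect of adding Days 11, 21 and 41**

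| | Now | With added tests |
|---|---|---|
| First on-drug test, TAK-935 | after 30 days | after 10 (Day 11) |
| First on-drug test, former placebo | after 54 days | after 10 (Day 41) |
| Longest on-drug interval without a test | 54 days | 44 days (Days 41-85) |
| On-drug tests, 20 completers, including Day 85 | 16x2 + 4x1 = 36 | 16x5 + 4x2 = 88 |
| Same, before Day 85 | 16x1 + 4x0 = 16 | 16x4 + 4x1 = 68 |

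The last two rows assume that all 20 subjects enter and complete Part 2, which is optional. They count samples and do not measure detection.

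**4. A change that starts at 200 mg BID.** Days at 300 mg BID before it has a result are now 10 (Days 21-30) for TAK-935 subjects in Part 1 and 44 (Days 41-84) for former placebo subjects. With tests on Days 21 and 41 this becomes the laboratory turnaround, provided the change already shows in that sample. The documents give no turnaround; I assume 1 to 5 days.

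**5. Lead time.** Day 11 to Day 21 is 10 days, or 6 to 14 with the visit windows. A Day 11 result would be back before the Day 21 step under the same assumption.

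**6. Blood volume**
- Added: 3 x (6 + 2) = 24 mL. The Table 9.a row totals sum to 240 mL, so the new total is 264 mL.
- Days 11 and 21: PK 8 + PD 16 + AED 4 = 28, plus 8 = 36 mL.
- Day 41: PK 4 + PD 8 + AED 4 = 16, plus 8 = 24 mL.
- The 71 mL maximum in 9.1.11 is Day 1: PK 16 + PD 32 + AED 4 + DNA 6 + RNA 5 + chemistry 6 + hematology 2 = 71.
- Section 9.1.11 states a study total of 230 mL against 240 mL in Table 9.a, so it needs correcting in any case.

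**7. SAP windows.** SAP 7.1.2 sets bounds at approximate midpoints and keeps the value closest to the scheduled day. The laboratory bounds in Table 7.a follow Appendix A: (1 + 31)/2 = 16 and (31 + 85)/2 = 58. A Day 21 value would share 17-58 with Day 31, and in Table 7.b a Day 41 value would share one window with Day 85, so both would drop out of by-visit summaries. With the added days the midpoints are (11 + 21)/2 = 16, (21 + 31)/2 = 26, (31 + 41)/2 = 36 and (41 + 85)/2 = 63. The existing vital-sign windows break at 53/54 instead of 63/64, so they should not be copied.

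**The case against.** **The 9.1.18.1 sentence may be only loose wording.** It sets the timing of the PK sample and can be read as applying where laboratory samples are due. Appendix A and Table 9.a agree with each other, and 9.1.11 makes Appendix A the schedule. This stands: a reader might infer that the protocol orders laboratory draws on Days 11, 21 and 41 and then omits them, but the text does not go that far. The sparse schedule may be deliberate.

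**Monitoring may exist elsewhere.** A reader might infer that no laboratory safety testing happens on drug before Day 31 or Day 85. The documents do not support that. Required monitoring is delegated to a laboratory manual not available here, unscheduled tests are possible, and early withdrawals have Final Visit tests.

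**The Day 21 review has other content.** Vital signs and ABC-C are scheduled on Days 11 and 21, physical and neurological examinations on Day 21, AE assessment at every visit, and phone calls 3 days after each dose change. The investigator, in consultation with the sponsor, may reduce the dose at any time. Unstable, clinically significant hepatic disease is excluded. The multiple-dose AEs described in 6.2.2.1 are neuropsychiatric, which these assessments address. This limits the gain but does not supply a chemistry or hematology value.

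**Extra tests do not fully meet the concern, and they affect an endpoint.** The Day 11 sample is taken on the day of the 200 mg BID step. No 200 mg BID result is in hand before 300 mg BID in Part 1, and former placebo subjects still reach 300 mg BID without an on-drug result. More tests also raise the chance of at least one markedly abnormal value. Some criteria are wide: the HDL limits in SAP Appendix A leave only 40 to 60 mg/dL unflagged. All of this stands and belongs among the costs.

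**Conclusion.** The point holds as a low-cost improvement. On the schedule as written, the Part 1 steps to 200 and 300 mg BID are taken with no scheduled on-drug chemistry or hematology, and so is the former placebo subjects' step to 300 mg BID. The first such test comes after 30 or 54 dosing days, and until then the 7.5 limits cannot act on a symptom-free change unless an unscheduled test is done. Adding tests at three existing draws brings both figures to 10.

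The gain is modest and the confidence medium. It rests on Appendix A being followed and on the laboratory manual adding nothing. Nothing here shows that TAK-935 carries a liver risk, or that escalation is unmonitored.

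**What to change.** **Protocol**
- Appendix A: mark serum chemistry and hematology on Days 11, 21 and 41, drawn with the PK/PD/AED samples. State in footnote (l) that urinalysis is not added on these days.
- Section 6.1: the investigator reviews available Day 11 results before the Day 21 increase. A missing or unusable Day 11 sample is repeated at Day 21 and reviewed on receipt; it does not block the increase. Day 21 and Day 41 results are reviewed on receipt, ideally by the phone call 3 days later.
- Table 9.a: chemistry and hematology become three samples in Part 1 and three in Part 2, total 264 mL. Match the total in 9.1.11.

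**SAP Tables 7.a and 7.b.** Separate laboratory tests from ECG, which keeps its windows. For laboratory tests use Visit 3 2-16, Visit 4 17-26, Visit 5 27-36, Visit 6 37-63 (in Table 7.b, day after first Part 2 dose to 63) and Visit 7 64 to Last Dose+7.

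**Cost.** A protocol amendment with IRB review and possible re-consent, and an SAP update. Each subject has three more panels (60 over 20 subjects), 24 mL more blood and, if possible, an overnight fast at three more visits. No visit, venipuncture, planned dose or stopping threshold changes. If subjects are already enrolled, report the number of tests per subject beside the markedly abnormal summaries.

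If the sponsor prefers the present schedule, the minimum is to limit the 9.1.18.1 sentence to days on which laboratory tests are scheduled, and to state any further monitoring that the laboratory manual requires.

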**Table 6.a Planned TAK-935 BID Doses and Associated Estimated EO Levels**

TAK-935 BID Dose (mg)	Average EO Level (%) (a)
300	85-95
200	80-90
100	70-80

(a) Average EO% at steady state during a dosing interval.

The investigator, in consultation with the sponsor, may decide to reduce the IP (TAK-935 or placebo) during Part 1 and TAK-935 during Part 2 dose at any time during the study, in the event of any safety or tolerability concerns. In Part 1, the planned starting dose of TAK-935 for adult subjects is 100 mg BID to achieve an average steady-state EO of approximately 70% to 80%. If well tolerated, this dose will be increased to 200 mg BID on Day 11 and subsequently to 300 mg BID on Day 21; the average steady-state EO at these doses are expected to be approximately 80% to 90% and 85% to 95%, respectively ([Table 6.a](#)).

In Part 2, the planned starting dose of TAK-935 for all subjects, including those who received placebo in Part 1, is 200 mg BID to be increased to 300 mg BID. The dose may be decreased at any time due to safety or tolerability concerns.

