**Table 8.a Planned Dose and Regimen**

Study Part	Planned Doses	Treatment Description
Part 1 (double-blind dose escalation)	TAK-935 200 mg/day (100 mg BID)	1 TAK-935 100 mg tablet BID for 10 days
	Matching Placebo BID	1 placebo tablet BID for 10 days
	TAK-935 400 mg/day (200 mg BID)	2 TAK-935 100 mg tablets BID for 10 days
	Matching Placebo BID	2 placebo tablets BID for 10 days
Part 2 (open-label dose escalation)	TAK-935 600 mg/day (300 mg BID)	3 TAK-935 100 mg tablets BID for 10 days
	Matching Placebo BID	3 placebo tablets BID for 10 days
	TAK-935 400 mg/day (200 mg BID)	2 TAK-935 100 mg tablets BID for 10 days
	TAK-935 600 mg/day (300 mg BID)	3 TAK-935 100 mg tablets BID for 44 days

Note 1: The dose of IP will be gradually escalated during Parts 1 and 2, provided there are no safety or tolerability concerns. At the end of Part 2, the dose of TAK-935 will be de-escalated before dosing is discontinued. See Section 6.1 for details of the dose escalation and de-escalation procedures.

Note 2: The investigator, in consultation with the sponsor, may reduce the IP (Part 1) or TAK-935 (Part 2) dose at any time in the event of any safety or tolerability concerns, including to the 100 mg BID dose in Part 2.

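### Part 2 restarts a subject at 200 mg BID on Day 31 even after a Part 1 cut to 100 mg BID for not tolerating 200 mg BID, with no review tied to that step

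*Protocol*

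**What the plan says.** **Part 1 reduction.** Under Protocol 6.1 the 200 mg BID level "may be reduced to 100 mg BID in subjects who cannot tolerate the 200 mg BID dose or demonstrate safety concerns". A subject reduced in this way "will stay on that dose level until the end of the Double-Blind Treatment Period", that is, to Day 30.

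**Part 2 start.** Anyone who completes Part 1 may continue. Protocol 6.1 then states that "all subjects will start on TAK-935 200 mg BID at the start of Part 2", and gives the reason: "Because some subjects may enter Part 2 after receiving placebo and others TAK-935 up to 300 mg BID and to maintain the study blind". Protocol 6.2.2.2, below Table 6.a, repeats that "the planned starting dose of TAK-935 for all subjects, including those who received placebo in Part 1, is 200 mg BID". Protocol 2.0 and SAP 4.4 carry the same rule. None of these places mentions a subject who ended Part 1 at 100 mg BID.

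**Checks tied to a day.** Protocol 6.1 requires a safety review and a benefit-risk discussion on Day 21 and on Day 41, before the step to 300 mg BID. Appendix A footnote (s) names Days 11, 21 and 41 as the days of increase and makes them conditional on safety and tolerability. It does not name Day 31.

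**General protections.** Note 1 to Table 8.a makes escalation in both parts conditional on safety and tolerability. Protocol 6.2.2.2 adds, for Part 2: "The dose may be decreased at any time due to safety or tolerability concerns". Note 2 to Table 8.a lets the investigator, in consultation with the sponsor, reduce the "dose at any time in the event of any safety or tolerability concerns, including to the 100 mg BID dose in Part 2".

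**The concern.** Within each part the protocol keeps a reduced subject at the lower level: to the end of the double-blind period in Part 1, and to the Final Visit in Part 2. Between the parts, the start rule lifts a subject at 100 mg BID back to the dose already judged too much for that person. The protection is a general condition and a reduction that the investigator may choose to make. The starting rule itself points the other way.

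This matters because safety and tolerability is the primary objective, Protocol 11.0 provides for no data safety monitoring committee, and many of these subjects may depend on a caregiver to report problems. The two reasons given for the common start, mixed prior exposure and the blind, do not require re-exposure of this subject.

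**Working it through.** The plan states no figure to reproduce here. The check sets the dosing rules side by side, then sizes the step.

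**1. What happens to each reduced TAK-935 subject (Protocol 6.1, Appendix A footnote (s))**

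| Last Part 1 level | Day 31 level | Next scheduled rise above the reduced level | Check tied to that day |
|---|---|---|---|
| 200 mg BID, reduced from 300 | 200 mg BID | Day 41, to 300 mg BID | Safety review and benefit-risk discussion; footnote (s) condition |
| 100 mg BID, reduced from 200 | 200 mg BID | Day 31, to 200 mg BID | None |

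Neither Part 1 reduction is carried through Part 2. The difference is that the scheduled return to 300 mg BID has a review in front of it, and the return to 200 mg BID does not. The Day 11 rise to 200 mg BID needs no benefit-risk discussion either, but it falls under the footnote (s) condition, and on Day 11 the subject has no history of failing that dose.

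**2. Size of the Day 31 step (Tables 6.a and 8.a)**

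- Before: 100 mg × 2 = 200 mg/day, 2 tablets a day, estimated average enzyme occupancy 70-80%.
- After: 200 mg × 2 = 400 mg/day, 4 tablets a day, estimated average occupancy 80-90%.
- Ratio of daily doses: 400 / 200 = 2.

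**3. Doses at 200 mg if nobody intervenes**

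- Days 31-33, before the day of the 3-day call: 3 × 2 = 6 doses, the first planned in clinic and 5 at home.
- Days 31-40: 10 × 2 = 20 doses.

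These are upper limits, since the dose can be cut on any of these days.

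**4. How many subjects**

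The documents give 16 TAK-935 subjects and no intolerance rate. For illustration only, let p be the share ending Part 1 at 100 mg BID and q the share of those who enter Part 2, both assumed. With r = p × q, the expected number is 16r and the chance of at least one is 1 − (1 − r)^16.

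| p | q | r | Expected number | Chance of at least one |
|---|---|---|---|---|
| 0.02 | 0.50 | 0.010 | 0.16 | 14.9% |
| 0.05 | 0.75 | 0.0375 | 0.60 | 45.8% |
| 0.10 | 0.75 | 0.075 | 1.20 | 71.3% |
| 0.20 | 1.00 | 0.200 | 3.20 | 97.2% |

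The spread shows that the number cannot be estimated from the documents.

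**5. Whether a different start would break the blind**

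Part 1 uses one, two or three matching tablets BID in both arms (Table 8.a), and the site already knows the blinded tablet level. A rule based on that level, applied alike in both arms, shows nothing about allocation.

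**The case against.** The best defence is that the protocol already lets the investigator avoid the problem. Going from 100 to 200 mg BID is an escalation, recorded intolerance is a tolerability concern, and Note 1 to Table 8.a conditions escalation on there being none. The Part 2 permission to drop to 100 mg BID does not ask for a second failure, so it could be used on Day 31 itself. The site that made the reduction sees the subject that day, with adverse events, vital signs, ECG, laboratory tests and the behavior checklist assessed and the morning dose planned in clinic. Entry to Part 2 is optional, and a phone call is due three days after an up-titration. Protocol 6.2.1 also gives the main goal as finding a safe and tolerable dose, so retrying a dose may be intended.

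Most of this stands, and it limits the harm. It does not supply a starting rule. Note 1 is general and sits under a table whose first Part 2 line is 400 mg/day. Protocol 8.1.3 has tablet counts follow the IVRS/IWRS, and Protocol 14.2 tells investigators not to deviate. One site could treat the common start as binding while another uses its discretion. If a retry is intended, it deserves the kind of review that precedes the Day 41 retry.

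One could also argue that the Part 2 sentence holding reduced subjects to the Final Visit covers a Part 1 reduction. It follows the Part 2 dosing steps, its Part 1 counterpart stops at the end of the double-blind period, and it cannot be squared with a start at 200 mg BID for everyone.

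Two stronger readings are tempting. A reader might infer that the protocol forces re-exposure; the conditional escalation and the reductions allowed at any time rule that out. A reader might also infer that Day 31 is the only place where a Part 1 hold lapses. It is not, because a subject reduced from 300 to 200 mg BID is scheduled for 300 mg BID again on Day 41.

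**Conclusion.** The point holds, at minor to moderate severity. The written default on Day 31 returns a subject who did not tolerate 200 mg BID to that dose, and no safety or benefit-risk check is attached to that day. For an affected TAK-935 subject the daily dose doubles, with up to 6 doses before the day of the phone call and up to 20 by Day 40 if no one acts. That investigators would not act is an assumption, and the documents give them several ways to do so.

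A high chance of at least one affected subject should not be inferred from the upper rows of the illustration: they rest wholly on assumed rates. The conclusion rests on the wording of the dosing rules and needs no rate.

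**What to change.** In Protocol 2.0, 6.1, 6.2.2.2, 8.1.3 and Appendix A footnote (s), and in SAP 4.4, state the following:

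- A subject whose final blinded Part 1 level was one tablet BID, in either arm, starts Part 2 at TAK-935 100 mg BID by default. All others start at 200 mg BID as now.
- The investigator may raise such a subject to 200 mg BID on or after Day 31, following a documented safety and benefit-risk review, with the 3-day phone call. Without that review the subject stays at 100 mg BID.
- The Day 41 step to 300 mg BID applies only to subjects then tolerating 200 mg BID.

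The existing Day 85 rule for subjects on 100 mg BID, which has no de-escalation, needs no change.

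The cost is a protocol amendment with IRB handling, re-signing of consent if the form is revised, and a change to IVRS/IWRS dispensing. The size of that last change cannot be judged, as the system manual is a separate document. No extra subjects, scheduled visits or tablet strengths are needed. Part 2 starting doses become slightly less uniform. A placebo subject reduced in Part 1 also starts at 100 mg BID until reviewed, which may cost a little higher-dose safety and PK data in a study of about 20 subjects.
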